#### Safety Population

The Safety population will consist of all subjects who received at least one dose of IP. This population will be used for all summaries of safety data. Subjects randomized to placebo who receive any dose of CC-93538 will be summarized in the CC-93538 group. Subjects randomized to CC-93538 who receive only placebo will be summarized in the placebo group; otherwise, they will be summarized in the CC-93538 group.

### **9.3 Sample Size and Power Considerations**

The sample size is based on two-sample t-test for the primary endpoint, changes in mean number of peak eos per hpf in GI biopsies from baseline to Week 16. The null hypothesis and the alternative hypothesis for the primary endpoint are as follows;

- Changes in mean number of peak eos from baseline at Week 16

Null hypothesis  $H_0: \mu_{CC-93538} = \mu_{Placebo}$

Alternative hypothesis  $H_a: \mu_{CC-93538} \neq \mu_{Placebo}$ ,

where  $\mu_{CC-93538}$  represents the true mean change value relative to CC-93538 and  $\mu_{Placebo}$  represents true mean change value relative to placebo.

Using this hypothesis, if the expected mean change in eos count in the active treatment group was -70, the expected mean change in eos count in the placebo group was 0, and the standard deviation (SD) was 70, the sample size necessary to achieve at least 80% power in a t-test at a significance level of 0.05 was calculated. Using a 2:1 ratio of active to placebo, 39 subjects are required. Assuming a Week 16 drop-out rate of approximately 10%, the goal is to enroll a total of 45 subjects.

The expected change from baseline in eos count in the active treatment group is based on the Phase 2 EoE study (Study RPC02-201); mean value at baseline for the CC-93538 360 mg treatment group of 139.4, and mean value at Week 16 of 31.3, with a percent change of approximately 80%. The baseline value in patients with EGE was assumed to be approximately 90 based on the results of studies of other drugs in patients with EGE (Dellon, 2020). Therefore, the expected change from baseline in eos in the active treatment group is assumed to be approximately 70. Change from baseline in eos count in the placebo group was assumed to be 0 based on the results of studies of other drugs (Dellon, 2020). With reference to the baseline GI eos count results of other drug studies of 52 (Dellon, 2020), the results of Study RPC02-201 in the CC-93538 360 mg group of 90, and the results of Study RPC02-201 in the CC-93538 180 mg group of 71, SD was assumed to be 70, which is approximately the mean of those values.

## **9.4 Background and Demographic Characteristics**

Summaries for the demographics, baseline characteristics, medical history, prior medication, and protocol deviations will be presented for the ITT population by treatment for the Induction Phase and by treatment and in total CC-93538 for the Maintenance Phase. Concomitant medications will be presented for the Safety population by treatment for the Induction Phase, and by treatment and in total CC-93538 for the Maintenance Phase. Individual listings will also be provided, including concomitant medical procedures for the Safety population.

## **9.5 Subject Disposition**

The disposition of subjects will be summarized with numbers and percentages by treatment for all randomized subjects. Summaries will include the number and percentage of subjects in the following categories:

- Never dosed, dosed, completed the study, permanently discontinued from IP, and discontinuation from the study
- Time to permanent discontinuation from IP and time to discontinuation from the study
- Primary reasons for discontinuation from the study

Subjects in each analysis population as defined in [Section 9.2](#) will be summarized with number and percentage.

## **9.6 Efficacy Analysis**

### **9.6.1 Efficacy Analysis of the Primary Endpoint**

#### **9.6.1.1 Intercurrent Event and Analysis Strategies**

The following are the intercurrent events (ICEs) of interest:

1. Treatment discontinuation in subjects without the use of concomitant rescue therapy or prohibited medication (subjects remain in the study)
2. The use of concomitant rescue therapy or prohibited medication which may impact the efficacy assessment for CC-93538
3. Treatment discontinuation followed by rescue therapy or prohibited medication which may impact the efficacy assessment for CC-93538

For intercurrent event (ICE) number 1, all observed data will be included in the primary analysis regardless of the occurrence of the ICE according to the respective endpoint definition. For ICE numbers 2 and 3, all observed data will be included in the primary analysis.

#### **9.6.1.2 Changes in Mean Number of Peak eos Count from Baseline to Week 16 (Induction Phase)**

The primary analysis will be conducted on the ITT population based on an analysis of covariance (ANCOVA) model with treatment group, concomitant steroid use (yes or no), and baseline eos count included in the model. The comparison between CC-93538 360 mg SC once weekly and placebo for change in number of peak eos count from baseline at Week 16 will be made using the difference in least squares mean (LSM) at a 5% 2-sided significance level. Point estimates for the mean difference between the two treatment groups using the LS mean changes and corresponding 95% Wald CI will be reported. In addition, LSMs (standard error [SE]), arithmetic means (SD), and arithmetic mean changes (SD) will be summarized by treatment group.

Missing data will be handled using a multiple imputation (MI) approach under a missing at random (MAR) assumption.

Sensitivity analyses will be performed to support the primary analysis and provide additional insights to understand the treatment effect. For the primary estimand analysis, robustness due to missing data MI under MAR assumption will be explored using tipping point analysis ([Yan, 2009](#); [Campbell, 2011](#); [Yuan, 2014](#)). In considering the ICEs of study interest (ie, ICE number 2, use of rescue therapy/prohibited medication, and ICE number 3, treatment discontinuation followed by use of rescue therapy/prohibited medication), an analysis using the hypothetical estimand strategy for change in eos count at Week 16 will be conducted.

## **9.6.2 Subgroup Analyses**

To assess whether the treatment effect is consistent across various groups, subgroup analyses will be performed for the primary endpoint at Week 16. Treatment differences and 2-sided 95% CIs

will be provided for each subgroup listed below. Forest plots for the treatment differences by subgroup will also be provided.

1. Concomitant steroid use (yes versus no)
2. Prior history of corticosteroid use for the treatment of EGE (yes versus no)
3. Age group (adolescents [12 to 17 years] versus adults [ $\geq 18$  years], non-elderly adults [ $< 65$  years] versus elderly adults [ $\geq 65$  years]).  
For EGID Severity Score, adolescents is set as 12 to 19 years
4. Sex (female versus male)

If there are not enough subjects within a subgroup enabling a valid statistical inference, the corresponding subgroup analyses will not be performed, and summary statistics will be provided instead.

### **9.6.3 Analysis of Secondary Efficacy Endpoints**

#### **9.6.3.1 Analyses Methods**

##### Continuous variables:

- Changes in mean number of peak eos count per hpf from baseline to Week 48
- Changes from baseline in each of 5 domain scores of the Izumo Scale (Weeks 14, 16, 32, and 48)
- Changes from baseline in total score of EGID Severity Score (Weeks 16, 32, and 48)
- Percent changes in mean number of peak eos per hpf in GI biopsies from baseline (Weeks 16 and 48)
- The time until concomitant corticosteroid treatment to zero (and continued by Week 48) (from Week 16 through Week 48)

The analysis for continuous variables of the secondary endpoints will be conducted on the ITT population using the ANCOVA model with treatment group (CC-93538 360 mg SC once weekly, CC-93538 360 mg SC once every other week, and placebo), prior steroid use (yes or no), and baseline values included in the model. Point estimates for the mean difference between the treatment groups using the LS mean changes and corresponding 95% Wald CI will be reported. The transition from the Maintenance Phase to the OLE Phase will be treated as ICE. Missing data and ICEs will be handled via the same strategy as for the primary analysis.

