### **1.3.2 Rationale for the Study Design**

The Phase 3 program includes a multicenter, Japan-local, randomized, double-blind, placebo-controlled induction and maintenance study to evaluate the efficacy and safety of CC-93538 in adult and adolescent subjects with EGE (Study CC-93538-EG-001). In addition, a multicenter, multinational, randomized, double-blind, placebo-controlled induction and maintenance study to evaluate the efficacy and safety of CC-93538 in adult and adolescent subjects with EoE (Study CC-93538-EE-001, the core Phase 3 study) with a separate, optional Open-label Extension Study (Study CC-93538-EE-002) are included.

The EGE study includes a 16-week Induction Phase followed by a 32-week Maintenance Phase, and an Open-label Long-term Extension (OLE) Phase for a minimum of 2 years. A double-blind, placebo-controlled treat-through design with allowance for use of concomitant corticosteroid therapy and concomitant rescue therapy has been chosen, as it enhances subject recruitment and retention for evaluation of relevant short-term as well as the long-term efficacy of CC-93538 in EGE. Since chronic administration of systemic steroids should be avoided as much as possible, the timing of the primary endpoint evaluation was set at 16 weeks, taking into account the timing at which the dosage of systemic steroids can be changed.

For the OLE Phase, the CC-93538 360 mg SC dose will be administered by a single injection of 2 mL provided in a 360 mg/2 mL [REDACTED] in Protocol Amendment 5. The results of Study CC-93538-CP-002 support the introduction of the new 360 mg/2.0 mL PFS presentation administered as a single injection in Protocol Amendment 4 (see [Section 1.2.2.5](#)). Further, Study IM042-003 Part 1 preliminary results demonstrated that the [REDACTED] presentation was biocomparable to the PFS presentation. The two presentations of CC-93538, given by PFS or [REDACTED] administered as a single dose of 360 mg, were well tolerated and had an acceptable safety profile in healthy adults. The ADA profiles were similar between subjects receiving the CC-93538 with the PFS or [REDACTED] with no differences in safety, tolerability, or PK. The results of Study IM042-003 support the introduction of the 360 mg/2 mL [REDACTED] presentation in Protocol Amendment 5.

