**Table 1: Study Objectives**

Primary Objective:
The primary objective of the study is to assess the efficacy of CC-93538 versus placebo in obtaining histologic improvement based on tissue eosinophils (eos) count at Week 16.
Secondary Objective(s)

The secondary objectives are:
 

• To assess the efficacy of CC-93538 versus placebo in reducing eosinophilic gastroenteritis (EGE)-related symptoms at Week 16

• To assess the efficacy and the persistence of effect of CC-93538 versus placebo at 48 weeks in:

– Obtaining histologic improvement based on tissue eos count in EGE

– Reducing EGE-related symptoms

• To assess the persistence of effect of CC-93538 through administration of a less frequent dosing regimen at 48 weeks in:

– Obtaining histologic improvement based on tissue eos count in EGE

– Reducing EGE-related symptoms

• To evaluate the safety and tolerability of CC-93538 including characterization of the immunogenicity profile throughout the study

• To evaluate the efficacy and the persistence of effect of CC-93538 versus placebo for 48 weeks in reducing concomitant corticosteroid use

• To evaluate the time to and frequency of EGE flare events and use of rescue therapy during the study

• To assess trough concentrations of CC-93538 in subjects with EGE

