### **3.1.3 Maintenance Phase**

After completion of Week 16 of the Induction Phase, eligible subjects will continue participation and enter the Maintenance Phase if none of the conditions disqualifying subjects from eligibility have been met as described in [Section 3.1.6](#). A placebo-controlled Maintenance Phase will allow for a determination of persistence of treatment effect and the overall long-term efficacy of CC-93538.

The Maintenance Phase treatment arms include CC-93538 360 mg SC once every week, CC-93538 360 mg SC once every other week, and matching placebo. Subjects who are randomized to receive CC-93538 360 mg SC once weekly in the Induction Phase will be re-randomized (1:1) to CC-93538 360 mg SC once weekly or CC-93538 360 mg SC once every other week at the beginning of the Maintenance Phase, and subjects who are randomized to receive matching placebo in the Induction Phase will continue placebo in the Maintenance Phase. A double-blind fashion will be kept in the Maintenance Phase.

If the reduction of EGE-related symptoms is observed at/after Week 16 (in the Maintenance Phase), the investigator should begin tapering the dosage regimen of concomitant corticosteroid treatment after Week 16. The dose reduction should be 2.5 mg/week (as the equivalent of prednisone). If the symptoms worsen after tapering of the dosage regimen of concomitant

corticosteroid treatment, the dose can be increased until it is the same as the baseline dose at the Induction Phase.

Subjects who complete Week 48 of the Maintenance Phase have 2 options:

1. to enter the Open-label Long-term Extension Phase (Section 3.1.4)
2. to return for an Interim and a Final Safety Follow-up Visit at 8 and 16 weeks, respectively, after the last dose of IP (at Week 55 and Week 63 for study completers) ([Section 3.1.5](#))

Subjects with a worsening of EGE symptoms (described in [Section 6.4.2.10](#)) during the Maintenance Phase will be required to complete the EGE Flare Assessment Visit per the Table of Events ([Table 5](#)). The subjects will need to discontinue participation in the Maintenance Phase and may be eligible to enter the OLE Phase. Details are described in Section 3.1.6.

Clinical laboratory tests, vital signs, physical examinations [REDACTED]  

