- A severe EGE flare is defined as any worsening of EGE symptoms including a high intensity episode resulting in an emergency department visit or hospitalization, with need for rescue therapy (eg, including but not limited to concomitant corticosteroid therapy over the baseline dose), or a worsening of EGE symptoms for 2 consecutive visits (4 weeks apart) resulting in the need for rescue therapy.
- A mild to moderate EGE flare is defined as any worsening of EGE symptoms without the need for rescue therapy. Concomitant use of systemic corticosteroid therapy with or under the baseline dose of concomitant corticosteroid treatment is not considered as rescue therapy.

During the OLE Phase, subjects who demonstrate a persistent lack of improvement or worsening of EGE symptoms should be evaluated to determine if continuing the study treatment is appropriate. While subjects will have the opportunity to continue participation in the OLE with use of rescue therapy as needed, based on clinical judgment, the investigator should discontinue any subject in which study participation no longer is in the best interest of the subject.

The ET visit or the OLE-ET/EoT procedures performed at the EGE Flare Assessment Visit do not need to be repeated for subjects who discontinue the study prematurely due to an EGE flare.

Subjects who are discontinued from the Induction Phase, the Maintenance Phase or the OLE Phase will be asked to complete an ET visit or an OLE-ET/EoT Visit ([Section 6.2.2](#) and [Section 6.3.2.2](#)) and the 2 Safety Follow-up Visits ([Section 6.3.1](#)).

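### Steroid dose at Week 48 depends on response and may differ by arm; state that the Week 48 effect includes the taper and report steroid-free response and dose by arm

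*Combined protocol and SAP*

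**What the plan says.** Table 1 sets a secondary objective: "To assess the efficacy and the persistence of effect of CC-93538 versus placebo at 48 weeks in" tissue eosinophils and symptoms. Table 2 makes the clinical-plus-histologic composite at Week 48 a key secondary endpoint.

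Background steroid is fixed to Week 16. Section 1.3.2 ties the primary time point to the moment when that dose may vary: "the timing of the primary endpoint evaluation was set at 16 weeks, taking into account the timing at which the dosage of systemic steroids". From Week 16, if symptoms have reduced, Section 3.1.3 says "the investigator should begin tapering the dosage regimen of concomitant corticosteroid treatment after Week 16. The dose reduction should be 2.5 mg/week" (prednisone equivalent). If symptoms then worsen, the dose may go back up to the baseline dose.

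Section 6.4.2.10 adds: "Concomitant use of systemic corticosteroid therapy with or under the baseline dose of concomitant corticosteroid treatment is not considered as rescue therapy". None of the three intercurrent events in Section 9.6.1.1 covers tapering, or staying on steroid, at or below the baseline dose.

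Section 9.6.3.1 lists "Changes in mean number of peak eos count per hpf from baseline to Week 48" first among its continuous variables. The ANCOVA for these variables has one yes/no steroid term, labelled as prior use. The responder analyses use a CMH test stratified by baseline concomitant corticosteroid. Section 9.6.2 splits results by steroid use, but its "subgroup analyses will be performed for the primary endpoint at Week 16". The hypothetical-strategy analysis in Section 9.6.1.2 is also for Week 16 only.

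**The concern.** Up to Week 16 the arms share the same steroid background in expectation. After that, the dose follows symptom response, which the drug is meant to change. If CC-93538 relieves symptoms more than placebo, more of its steroid users should taper. If steroid also suppresses tissue eosinophils, the Week 48 contrast among those users mixes the drug effect with a difference in background treatment.

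The plan does not say which effect Week 48 persistence means: that of the regimen with its taper, or that at equal steroid dose. A modest Week 48 difference could then reflect fading efficacy or successful steroid sparing, and no specified table joins the two. In the composite, a responder still on steroid counts the same as one who is steroid-free. Izumo domains, histologic response and eosinophil change at Week 48 share the problem, for both CC-93538 regimens. The Week 16 primary analysis does not, because the dose is held stable until then.

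**Working it through.** **1. The plan's own figure.** Section 9.3 assumes mean changes of -70 and 0, SD 70, 2:1 allocation and "at least 80% power in a t-test at a significance level of 0.05"; Section 9.6.1.2 tests "at a 5% 2-sided significance level". Exact two-sample t-test power (noncentral t) is 78.5% at 24+12 = 36 subjects and 81.8% at 26+13 = 39, so 39 reproduces. Allowing 10% drop-out, 39/0.9 = 43.3, so 44; the next multiple of three is 45. No power is stated for Week 48.

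**2. Week 48 reference.** About 30 CC-93538 subjects split 1:1 give about 15 per regimen against 15 placebo, before losses. Carrying over a difference of 70 and SD 70, t-test power at 15 v 15 is 75.3%.

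**3. Time to zero steroid.** 10 mg / 2.5 mg per week = 4 weeks. A subject starting at Week 16 from the highest permitted dose could be at zero by Week 20, with 28 of the 32 Maintenance weeks remaining.

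**4. Attenuation relative to equal background.** Let s be the share on steroid at baseline, d the fraction tapered on CC-93538 minus that on placebo, and e the rise in eos/hpf from tapering. The documents give none of these; all are assumptions.

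Attenuation = s × d × e; difference = 70 − attenuation.

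| s | d | e | Attenuation | Difference | Power, 15 v 15 |
|---|---|---|---|---|---|
| 0.25 | 0.2 | 10 | 0.5 (0.7%) | 69.5 | 74.7% |
| 0.5 | 0.4 | 20 | 4 (5.7%) | 66 | 70.3% |
| 0.75 | 0.6 | 40 | 18 (25.7%) | 52 | 50.2% |
| any | 0 | any | 0 | 70 | 75.3% |
| 0.5 | −0.2 | 20 | −2 | 72 | 77.6% |

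Within steroid users alone the loss is d × e. In the first three rows that is 2, 8 and 24, leaving 68, 62 and 46 of 70.

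**5. A separate pull toward zero.** Section 9.6.3.1 treats the move to OLE as an intercurrent event handled as in the primary analysis, which uses all observed data. If a fraction q of placebo subjects contributed Week 48 values on open-label drug at full effect (an assumption), the difference is 70 × (1 − q): 63, 56 or 49 for q = 10%, 20% or 30%.

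**6. Who can be a responder on steroid.** Entry requires at least 4/15 in one Symptom of Interest (Section 4.2). Clinical response requires under 4/15 in all three (Section 9.6.3.1). Every clinical responder has therefore improved and should have begun tapering. Those still on steroid at Week 48 are late improvers, subjects returned to the baseline dose, or subjects not tapered as planned.

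**7. Precision by stratum.** If 30% to 70% of subjects are steroid users (assumed), the without-steroid stratum holds 15 × 0.3 to 15 × 0.7, about 5 to 10 per arm. Power at the full effect is then about 29% to 56%.

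**The case against.** A reader might infer that Week 48 simply compares CC-93538 on reduced steroid with placebo on continued steroid, and so understates persistence. The documents do not support that.

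- **Exit rules limit the contrast.** Section 6.4.2.10 counts at least 4 weeks without change as worsening. Section 6.4.2.11 bars such subjects from Maintenance, and Section 3.1.6 has them leave it later, with possible OLE entry. Few unimproved placebo subjects should reach Week 48 on placebo plus full-dose steroid. Placebo subjects who improve fall under the same taper rule. This stands. It does not remove the imbalance: a subject who tapers, worsens and returns to the baseline dose can continue with no intercurrent event.
- **Understatement depends on the estimand.** The objective does not specify constant steroid dose, and Section 1.3.2 describes a treat-through design that allows concomitant steroid. For the regimen including the taper there is no bias. This stands, and it is why the plan should say which effect it means.
- **Steroid reduction has its own endpoints.** The proportion at zero dose (Weeks 24, 32, 40 and 48) and time to zero are planned. They are analysed separately, and none asks whether a responder is steroid-free.
- **The size is assumed.** Steroid users qualify with at least 30 eos/hpf while on stable steroid, so a large rise on tapering cannot be presumed. A reader might also expect little or no difference left among steroid users; even the largest scenario leaves 46 of 70.
- **Limits of the text.** Section 9.1 defers detail to the SAP, and some endpoint rows are redacted. No Week 48 provision of this kind appears in the available text. Week 48 p-values are nominal in any case.

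**Conclusion.** The point holds as a cheap improvement to a secondary objective. Steroid dose at Week 48 is a post-randomisation outcome that may differ by arm, and neither the intercurrent-event list nor the Week 48 models account for it. Relative to equal background, the difference is pulled toward zero only if CC-93538 subjects taper more and steroid lowers eosinophils.

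The assumed scenarios give a loss from under 1 to about 18 eos/hpf out of 70, none at equal taper rates, and an overstatement if placebo tapers more. They also assume that the Week 16 effect and SD carry over to Week 48 and that about 15 subjects per arm remain. The case for action does not rest on a particular size: as specified, the results could not tell a small difference due to steroid sparing from loss of effect.

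**What to change.** Leave the taper rule unchanged. In Section 9.6.3.1, state that the main Week 48 analysis estimates the effect of the regimen including the taper. Add, as supportive and nominal:

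1. Among subjects on steroid at baseline, Week 48 clinical, histologic and composite response with a concomitant steroid dose of zero.
2. Week 48 eosinophil, Izumo and response results by the baseline concomitant-steroid randomisation stratum. These should be descriptive where numbers are small, in line with Section 9.6.2, and not the basis for the persistence conclusion.
3. Prednisone-equivalent dose by arm and visit from Week 16 to Week 48.

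Also reconcile the steroid term. The Week 48 ANCOVA names prior steroid use, while the stratification factor (Section 9.1) and the primary model (Section 9.6.1.2) use concomitant steroid use. Section 9.6.2 lists prior history and concomitant use as separate subgroups.

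The cost is some wording and a few more tables from data already collected (stratum and concomitant therapy), best settled before the primary database lock. The downside is imprecise stratum estimates.
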